Because the incidence and severity of the individual major complications vary considerably, we will analyze morbidities in a multivariate (one record per outcome per patient) analysis instead of a collapsed composite approach. A multivariate approach allows us to capture information regarding individual morbidities and the correlation between morbidities.

The average relative effect of lactated Ringer's solution versus saline will be assessed across the five categories of major complications using generalized estimating equations (GEE) 'distinct effects' model with an unstructured working correlation matrix.⁵¹ To assess heterogeneity of the fluid effect across components of the primary outcome, we will assess the treatment-by-component interaction in a distinct effects GEE model. We will assess whether the average component-specific treatment effect was equal to zero using an average relative effect test. However, if the baseline incidences are either quite different from each other or if some are very small (say < 1%), will instead use the common effect GEE test. All analyses will adjust for unbalanced potentially confounding baseline characteristics.

Secondary analysis

The economic evaluation will be conducted from the hospital/payer perspective to determine the optimal strategy for economic outcomes between the two interventions. The evaluation will determine the incremental costs between the two interventions; uncomplicated care and care of complications, as well as a combined incremental cost. An example analysis is listed below showing the incremental difference between the interventions for various outcomes for standard care and complications. A cost is assigned to each outcome and a total cost per patient calculated.

Standard Care - Example

	Intervention A	Intervention B	Incremental Dif.	Estimated Cost	Total Cost
LOS	1	0.8	0.2	100	20
Electrolyte Measures	10	8	2	10	20
Electrolyte Replacement	2	1	1	20	20
				Total Cost/pt	60

Complications - Example

	Intervention A incidence	Intervention B incidence	Incremental Dif.	Estimated Cost	Total Cost
MI	0.1	0.05	0.05	10,000	500
DVT	0.2	0.1	0.1	1000	100
Pneumonia	0.3	0.2	0.1	2000	200
				Total Cost/pt	800

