We will use an overall alpha of 0.05 for both the primary and secondary/tertiary analyses, using a significance criterion of 0.05 for the primary analysis and 0.006 for each secondary/tertiary analysis (i.e., 0.05/8; Bonferroni correction). SAS Version 9.3 (SAS Institute, Cary, NC, USA) and R statistical software version 2.15.3 (R Project for Statistical Computing, Vienna, Austria) will be used for the analyses.

Pilot patients

We will enroll at least 5 pilot patients to test the feasibility of protocol adherence and data collection.

Interim analyses

At each quarter of the maximum enrollment (8,548), we will conduct an interim analysis to assess for efficacy and futility of using lactated Ringer's solution versus saline on our composite of major complications. The interim analysis will use the gamma spending function with parameters -4 for alpha (efficacy) and -1 for beta (futility). Boundaries for efficacy (futility on parentheses) at each stage are $P \leq 0.00160$ ($P > 0.92646$), $P \leq 0.00482$ ($P > 0.62368$), $P \leq 0.01472$ ($P > 0.2011$), and $P \leq 0.04404$ ($P > 0.04404$), respectively.

Sample size

Based on a preliminary query of the PHDS database, we found the incidence of complications among all patients who would have met the inclusion/exclusion criteria for this study:

Outcome	No. Missing	Overall Incidence (%)	Estimated Saline
----------------	--------------------	------------------------------	-------------------------

		(N = 12,182)	Incidence (%)
In-hospital mortality	0	65 (0.53)	0.59
Renal (AKI classification > 1)	0	213 (1.75)	1.94
Respiratory	90	285 (2.34)	2.60
Infectious	83	2895 (23.76)	26.40
Hematologic	83	311 (2.55)	2.83

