This study is designed to have about 90% power at the 0.05 significance level to detect a 20% relative decrease in major complications LR versus saline. We estimated the incidence of complications in the control group (saline) assuming that the two groups average out to the overall incidence. Sample size was calculated assuming a conservative correlation of 0.3 between outcomes. We estimated sample size using the MULTBINPOW SAS macro, which can estimate power for average relative effect GEE models given varying correlations and sample sizes (Mascha EJ Power Calculations for Tests on a Vector of Binary Outcomes (MULTBINPOW)).⁵¹ Cleveland Clinic Statistical Software Series 10 edn Cleveland; 2011: SAS program uses simulations to compute and display comparative power of several parallel-group multivariate tests for treatment effect on a vector of binary events.⁵² After accounting for 3 interim analyses and 1 final analysis, we will need to enroll a maximum of 8,548 patients for this study. If the Average Relative Effect analysis proves insufficient, we expect to nonetheless have > 99% power to detect a 20% relative increase in major complications in saline versus LR using either the collapsed composite or common effect GEE methods.

However, it is likely that the study would stop early. The table below provides boundary crossing probabilities for possible true underlying treatment effects: Null (no effect), Alternative (20% relative increase), half-way between the null and alternative, and 1.5 times the alternative effect. If the alternative hypothesis were true, the probability of crossing either the efficacy or futility boundary would be a cumulative 40% and 78% at interim analyses 2 and 3 (see “Alternative” row). Thus, there would be a 40% chance of stopping the study after N = 3,420 patients and 78% chance when N = 6,668 patients were enrolled if the alternative hypothesis is true. With an estimated 6,240 eligible patients available every year, we can expect this study to take a maximum of 1.37 years.

Expected Cumulative Boundary Crossing Probabilities (i.e., boundary crossing probabilities for either efficacy or futility)					
Effect*	Expected Crossing Stage	Boundary Crossing Probabilities			
		Interim 1	Interim 2	Interim 3	Final
Null	2.7	0.08	0.42	0.84	1.0
Alternative	2.7	0.09	0.40	0.78	1.0
½ Null, Alternative	3.0	0.06	0.28	0.63	1.0
Alt x 1.5	1.9	0.29	0.81	0.98	1.0

* True treatment effect in the population

Internal pilot study

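### The stated power of about 90% for the average relative effect test at 8,548 patients does not follow from the protocol's own inputs: five components give at most 81–85% before interim looks and 76–81% with them

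*Protocol*

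**What the plan says.** Under Sample size the protocol states that the study is "designed to have about 90% power at the 0.05 significance level to detect a 20% relative decrease in major complications LR versus saline". It adds: "Sample size was calculated assuming a conservative correlation of 0.3 between outcomes". The calculation used simulation software for average relative effect GEE models and led, after three interim looks and a final analysis, to a maximum of 8,548 patients. Saline incidences were obtained by "assuming that the two groups average out to the overall incidence".

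Under Primary analysis the effect "will be assessed across the five categories of major complications", by an average relative effect test. The same paragraph switches to the common effect GEE test if baseline incidences differ a lot or some are very small, with 1% as the example. Sample size claims more than 99% power for the collapsed composite or common effect test should the average relative effect analysis prove insufficient.

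The composite is not listed consistently. The Outcomes section names four components (renal, respiratory, infectious, hemorrhagic). The Primary outcome section adds in-hospital mortality, Primary analysis counts five categories, and the incidence table has five rows.

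**The concern.** The average relative effect test gives each component's log odds ratio equal weight. Mortality, at 0.59% under saline, therefore has one fifth of the weight, although only about 25 and 20 deaths are expected in the two arms. Such a test should be imprecise at this sample size, and positive correlation between components makes it more so.

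At stake are the power sentence, the basis for 8,548, and the early-stopping statements (40% and 78% cumulative crossing at the second and third interim), which rest on the same assumed drift.

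**Working it through.** **Inputs.**
- Saline rates from the Sample size table: 0.59, 1.94, 2.60, 26.40 and 2.83%. If LR = 0.8 × saline, the overall rate is 0.9 × saline; 23.76/0.9 = 26.40 and 0.53/0.9 = 0.59, so the table reproduces.
- Risk ratio 0.80 on every component.
- 4,274 per arm. The ratio is not stated; 1:1 is assumed from the equal alternating periods.
- Two-sided 0.05, from "using a significance criterion of 0.05 for the primary analysis". Sidedness is not stated in words. Read as two-sided, the printed P boundaries give an overall alpha of 0.050 with non-binding futility.

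**The protocol's own table first.** I applied the printed P boundaries at information 0.25, 0.5, 0.75 and 1.
- Drift 0: cumulative crossing 0.075, 0.418, 0.838 (printed 0.08, 0.42, 0.84).
- Drift 3.46: crossing 0.09, 0.40, 0.78, exactly the Alternative row, with 90% power.
- Half and 1.5 times that drift give 0.06, 0.28, 0.63 and 0.29, 0.81, 0.98, also as printed.

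The boundaries are sound, and the non-null rows assume an expected final Z of 3.46.

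**What the five-component test supplies (logit scale).**

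Per component, log OR = logit(0.8p) − logit(p), and Var = 1/(n p q) summed over the two arms.

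| Component | log OR | Var |
|---|---|---|
| Mortality | −0.2243 | 0.0897 |
| Renal | −0.2271 | 0.0276 |
| Respiratory | −0.2285 | 0.0207 |
| Infectious | −0.2924 | 0.0026 |
| Hematologic | −0.2290 | 0.0191 |

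Mean log OR = −0.240. At zero correlation the variances sum to 0.1597, so SE = √0.1597/5 = 0.0799, Z = 3.01, and power = Φ(3.01 − 1.96) = 85%. Mortality contributes 0.0897/0.1597 = 56% of the variance. With correlation, each arm adds covariances ρ × SE_j × SE_k.

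| Meaning of correlation | Z logit / log | Fixed power, log–logit | With printed boundaries (futility binding) |
|---|---|---|---|
| zero | 3.01 / 2.84 | 81–85% | 76–81% |
| latent 0.3 | 2.78 / 2.63 | 75–79% | 70–74% |
| pairwise 0.3, capped | 2.21 / 2.09 | 55–60% | 50–54% |

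Simulated trials on the logit scale gave 86%, 81% and 59% without looks, within two points of the formula.

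**The correlation input.** For two binary outcomes with rates a < b, the largest possible correlation is √[a(1−b)/(b(1−a))]. With infection at 26.40% this is 0.129 for mortality, 0.235 renal, 0.273 respiratory and 0.285 hematologic. A pairwise 0.3 is therefore impossible for every pair that includes infection. The capped row uses these maxima in the saline arm and the corresponding maxima in the LR arm.

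**Where 90% can be found.** I dropped mortality, as the Outcomes section does:
- latent 0.3: 89–92% fixed and 85–89% with the boundaries (log–logit);
- zero correlation, log scale: Z = 3.47, 93.5% fixed and 90% with the boundaries, which matches the Alternative row;
- pairwise 0.3, capped: 75–80% fixed and 70–75% with the boundaries.

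**The case against.** The strongest reply is that the average relative effect test may not be the test that is used. The planning rates meet both switching conditions under Primary analysis: mortality is below 1%, and 26.40/0.59 is about 45-fold. If rates turn out as planned, the common effect test becomes the primary test. An information-weighted common log odds ratio on the same inputs has an expected Z of about 4.9 (pairwise 0.3, capped) to 6.3 (zero correlation), and 99.3–99.9% power with the printed boundaries. This stands, and it bears out the protocol's claim of more than 99%.

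It also limits what may be inferred. A reader might conclude that a null primary result would come from an underpowered trial. The protocol does not support that, because its own rule points to a test with ample power. A reader might also want the table rebuilt on the weaker drift alone, but that would misdescribe the analysis most likely to be used.

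A second reply is that the software may treat 0.3 as a latent correlation, so 54% should not be presented as the true power. This also stands: the protocol does not say which correlation is meant. The latent reading still falls short of 90% for five components.

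The internal pilot does not help. It responds to incidences that differ from planning, whereas the shortfall arises when they are exactly as planned.

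**Conclusion.** The concern holds for the average relative effect test. With five components, a 20% relative decrease, two-sided 0.05 and 8,548 in total, no non-negative correlation gives about 90%. The ceiling is 81–85% without looks and 76–81% with the printed boundaries. At the stated 0.3, power with the boundaries is 70–74% (latent) or 50–54% (pairwise, capped). These figures assume 1:1 allocation, independent patients, and futility bounds that are followed.

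The likely sources are the four- versus five-component inconsistency and the undefined correlation, although the protocol does not allow this to be confirmed. The finding concerns the power statement and the table built on it. It does not show that the trial as a whole lacks power or must enrol more patients. A reader might add that clustering by two-week period lowers power further, but the protocol gives no between-period variance from which to quantify that.

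**What to change.** 1. State the number of components in the primary composite, and make Outcomes, Primary outcome, Primary analysis and Sample size agree.
2. Say whether 0.3 is a latent or a pairwise correlation, and use values attainable at the tabulated rates.
3. Re-run the power of the average relative effect test with the four-look boundaries, and replace the 90% by the result (no more than about 81% for five components).
4. Given the switching rule, state which test the 8,548, the power figure and the boundary-crossing table refer to. Rebuild the non-null rows and the 40% and 78% stopping statements on that test's drift.

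The cost is a repeated simulation, a revised paragraph and a revised table. No extra patients are needed. The downside is a less favourable stated power for the average relative effect test.

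### The patient counts given for interim analyses 2 and 3 (3,420 and 6,668) are the stopping probabilities multiplied by 8,548; the quarterly schedule puts these looks at 4,274 and 6,411

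*Protocol*

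**What the plan says.** The Interim analyses section of the protocol fixes the timing: "At each quarter of the maximum enrollment (8,548), we will conduct an interim analysis". It specifies gamma spending functions with parameters −4 (efficacy) and −1 (futility) and prints a pair of P-value boundaries for each of four stages. The Sample size section confirms the count of looks: "After accounting for 3 interim analyses and 1 final analysis, we will need to enroll a maximum of 8,548 patients for this study".

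The Sample size section then discusses early stopping. For a true effect equal to the design alternative, it says the probability of crossing either boundary "would be a cumulative 40% and 78% at interim analyses 2 and 3". That agrees with the Alternative row of the table below it (0.09, 0.40, 0.78, 1.0). The next sentence turns these probabilities into patient counts: "there would be a 40% chance of stopping the study after N = 3,420 patients and 78% chance when N = 6,668 patients" were enrolled.

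**The concern.** The same two looks are given two different sizes. Under the quarterly rule, interims 2 and 3 fall at one half and three quarters of 8,548. The Sample size text attaches their stopping probabilities to 3,420 and 6,668, which are 40% and 78% of 8,548.

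Two things are at stake. First, the early-stopping forecast is wrong as stated: the second look comes later than readers are told, and the third slightly earlier. Second, these are the only explicit patient counts that the protocol gives for the interim looks; the quarterly sizes have to be worked out. Someone scheduling a data cut could take 3,420 as the second look and apply boundaries that belong to half of the information.

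**Working it through.** **Inputs.** From Interim analyses: maximum enrolment 8,548, looks at each quarter, efficacy boundaries P ≤ 0.00160, 0.00482, 0.01472, 0.04404, and futility boundaries P > 0.92646, 0.62368, 0.2011, 0.04404. From Sample size: about 90% power, significance level 0.05, the crossing-probability table, the counts 3,420 and 6,668, and 6,240 eligible patients a year. One assumption is needed: the P-value boundaries are read as two-sided.

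**Step 1. Reproduce the printed counts.** Multiply each cumulative crossing probability by the maximum enrolment and round up:
- 0.40 × 8,548 = 3,419.2, giving 3,420
- 0.78 × 8,548 = 6,667.4, giving 6,668

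Both match exactly.

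**Step 2. Counts under the stated schedule.** Look k falls at (k/4) × 8,548:

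| Look | Quarterly schedule | Printed count | Difference |
|---|---|---|---|
| Interim 1 | 2,137 | none | – |
| Interim 2 | 4,274 | 3,420 | −854 (−20.0%) |
| Interim 3 | 6,411 | 6,668 | +257 (+4.0%) |
| Final | 8,548 | 8,548 | 0 |

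**Step 3. Which timing do the 40% and 78% belong to?** The printed boundaries were applied to the usual group-sequential normal process, with the standardised effect at full information (the drift) set to give 90% power at quarterly looks. That drift is 3.46. Cumulative probability of crossing either boundary with quarterly looks:

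| True effect | Computed, interims 1 / 2 / 3 | Protocol table |
|---|---|---|
| Null | 0.075 / 0.418 / 0.838 | 0.08 / 0.42 / 0.84 |
| Alternative | 0.094 / 0.400 / 0.779 | 0.09 / 0.40 / 0.78 |
| Halfway | 0.062 / 0.280 / 0.632 | 0.06 / 0.28 / 0.63 |
| 1.5 × alternative | 0.290 / 0.810 / 0.983 | 0.29 / 0.81 / 0.98 |

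All four rows agree to the precision printed. The 40% and 78% are therefore the probabilities at 4,274 and 6,411 patients.

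**Step 4. What if the looks were taken at the printed counts?** These are information fractions of 3,420/8,548 = 0.40 and 6,668/8,548 = 0.78. With the same boundaries and drift:
- Under the alternative, cumulative crossing is 0.094 / 0.325 / 0.805, so about 33% rather than 40% at interim 2 and about 80% rather than 78% at interim 3.
- Power is 0.890 rather than 0.900.
- The two-sided rejection rate under the null is 0.043, against 0.044 with quarterly looks.

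The printed boundaries would also no longer follow the stated spending function. With gamma parameter −4, cumulative alpha at fraction t is 0.05 × (1 − e^(4t)) / (1 − e^4). This is 0.0060 at t = 0.50 but 0.0037 at t = 0.40.

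**Step 5. Calendar effect.** At 6,240 patients a year, interim 2 falls at 4,274/6,240 × 12 = 8.2 months; the printed count implies 3,420/6,240 × 12 = 6.6 months.

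**The case against.** The best reply is that the operative rule is not in doubt. Only the Interim analyses section prescribes when looks occur. The sentence in Sample size describes expectations and schedules nothing. No boundary, table entry, power figure, maximum enrolment or duration (8,548/6,240 = 1.37 years) depends on 3,420 or 6,668. The power and alpha consequences in step 4 arise only if someone ignores the quarterly rule and keeps the printed P values; even then type I error stays below 0.05 and power drops by about one point, within the stated approximate 90%. The explanation of how the counts arose is also an inference, since the document does not give their derivation.

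Most of this stands. It limits the consequence: this is no threat to the validity of the primary test, and the stopping probabilities themselves are correct. It does not remove the contradiction. Rounding or enrolment overrun cannot explain a second look placed 854 patients before the planned one, and the sentence assigns the design a property that it does not have. Two exact matches in step 1 make the inferred cause very likely, but the finding does not need it.

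**Conclusion.** The concern holds. The counts 3,420 and 6,668 contradict the protocol's own schedule and should read 4,274 and 6,411. At 3,420 patients under the design alternative only interim 1 would have occurred, so the cumulative chance of having stopped would be about 9%, not 40%.

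The error is confined to two numbers in explanatory text and does not affect the design as specified under Interim analyses. It deserves correction because it concerns the timing of a stopping rule. The contradiction and its size rest on the protocol's figures alone. The reproduction of the crossing table rests on reading the boundaries as two-sided and calibrating the effect to 90% power; agreement in all four rows supports both.

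**What to change.** In Sample size, replace 3,420 by 4,274 and 6,668 by 6,411. It would also help to state the four look sizes (2,137, 4,274, 6,411 and 8,548) once under Interim analyses, so that nobody has to derive them; this second step is a convenience and not needed to remove the contradiction. The cost is two corrected numbers, plus one short list if it is adopted. Boundaries, crossing table, maximum enrolment and projected duration stay as they are.

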In summary, no compelling studies identify substantive harm from use of normal saline rather than lactated Ringer's solution in routine clinical practice or in the perioperative setting. Consequently, Guidet et al concluded that there is no convincing evidence that the mild hyperchloremic acidosis that occurs with infusion of normal saline is associated with detrimental effects on renal function, coagulation status, need for blood transfusion, and overall morbidity and mortality in perioperative setting.¹⁴ Animal studies and mostly retrospective data suggest that normal saline provokes a mild and transient hyperchloremic metabolic acidosis, which in turn can increase incidence of kidney injury and postoperative morbidity. However, there is no evidence that the mild acidosis that results from

normal saline administration results in kidney injury, especially with volumes used in typical clinical situations.

Objectives and Hypotheses

Perioperative volumes of saline cause a mild acidosis compared with buffered fluids. On the other hand, saline administration maintains plasma osmolality and better repletes vascular volume which is an important goal of perioperative fluid administration. Currently, there is no convincing evidence that either saline or buffered solutions are preferable. Consequently, both types of fluid remain in common use at the Clinic and worldwide.

There has never been a large trial of perioperative saline and balanced salt solutions comparing the incidence of major complications including acute kidney injury. Our primary objective is thus to determine the relative safety of perioperative saline and lactated Ringer's solution. Specifically, we propose to test the:

1. Primary hypothesis that a composite of major in-hospital postoperative complications is lower in patients given lactated Ringer's solution compared to normal saline.
2. Secondary hypothesis that acute kidney injury, measured by AKIN criteria, is lower in patients given lactated Ringer's solution compared to normal saline.

The acquisition cost of saline and lactated Ringer's solutions is similar in the United States. (Curiously, buffered solutions are far more expensive than saline in Great Britain.) But to the extent that one fluid or the other provokes more complications, cost of care may be increased with that fluid selection. Cost may also be increased by the need for additional electrolyte monitoring and electrolyte replacement.

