Before the first interim analysis (at approximately 1,000 patients), an internal pilot study for sample size extension may be proposed if the observed incidence of any complication differs considerably from the estimated incidence (i.e., original sample size estimates above fall outside the 95% CI for the estimated internal pilot study incidence). A second stage with new stopping boundaries would be designed with sample size and planned interim analyses to detect a 20% increase in complications based on the revised control group incidence.

Human subjects

The proposed study is primarily for the purpose of quality improvement and cost reduction, although the results may be sufficiently interesting to publish. We will use a non-randomized alternating treatment design in which each fluid regimen will be used for successive 2-week periods in designated physically distinct surgical units.

Evidence and current clinical practice support that crystalloids, both lactated Ringer's and normal saline, are clearly safe; furthermore, both are widely used in perioperative patients. However, each has potential advantages and disadvantages, and potentially different costs of care. We do not propose obtaining informed consent for the proposed quality project since both fluids are widely used in clinical practice and there is currently no compelling reason to believe one is superior to the other.

The project will coincide with another ongoing project “Supplemental Oxygen in Colorectal Surgery: A Quality Improvement Project” in colorectal surgery department in which intraoperative usage of oxygen is prospectively standardized between 2 alternating groups (30% vs. 80%). Surgical site infection is the primary outcome. Some patients in the proposed SOLAR study will also be enrolled in the ongoing study of Supplemental Oxygen.

Although an interaction between fluid choice and oxygen therapy is possible, one seems highly unlikely because the putative mechanisms of each differ. Furthermore, we will stagger group enrollment for this study versus the Oxygen study, starting enrollment in the middle of an Oxygen study 2-week period, so that fluid and oxygen interventions will be fully balanced for those patients whose enrollment overlaps with both studies, as in a factorial-design trial.

Significance

The study we propose will determine whether normal saline or buffered salt solutions are superior for intraoperative vascular volume repletion during major non-cardiac surgery.

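### The internal pilot would resize the trial for a 20% increase on the control incidence, although the trial is designed for a 20% decrease with lactated Ringer's versus saline

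*Protocol*

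**What the plan says.** Objectives and Hypotheses states the direction: "a composite of major in-hospital postoperative complications is lower in patients given lactated Ringer's solution compared to normal saline".

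The Sample size section gives "about 90% power at the 0.05 significance level" "to detect a 20% relative decrease in major complications LR versus saline", with a maximum of 8,548 patients. It names the reference arm and how its rate was found: "We estimated the incidence of complications in the control group (saline"), taking the two arms to average to the overall rate.

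Three later statements word the effect as an increase:

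- Sample size, back-up analyses: more than 99% "power to detect a 20% relative increase in major complications in saline versus LR".
- Sample size, introduction to the boundary crossing table: "Alternative (20% relative increase"), with no reference arm.
- Internal pilot study: if incidences at about 1,000 patients differ considerably from those planned, a second stage with new stopping boundaries may be designed "to detect a 20% increase in complications based on the revised control group incidence".

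Nothing in the protocol reconciles these wordings.

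**The concern.** The internal pilot sentence is the protocol's only rule for resizing the trial and rebuilding its boundaries, and it does not carry over the effect on which the trial was designed. A 20% decrease from saline is RR 0.80. A 20% increase on the control incidence is RR 1.20. Saline 20% above LR is RR 0.833; the reciprocal of a 20% decrease is a 25% increase, because 1/0.80 = 1.25. These three effects need different numbers of patients. A statistician who applied the sentence as written would size the second stage for an effect that nobody planned. One who noticed the conflict would have to choose an effect after data had begun to accrue.

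**Working it through.** **1. Which effect was planned?** If saline has incidence p and LR has RR × p, the average is p(1 + RR)/2. The printed overall incidences (%) then imply these saline incidences:

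| Component | Overall | Printed saline | RR 0.80: overall/0.9 | RR 0.833: overall × 1.2/1.1 | RR 1.20: overall/1.1 |
|---|---|---|---|---|---|
| Mortality | 0.53 | 0.59 | 0.59 | 0.58 | 0.48 |
| Renal | 1.75 | 1.94 | 1.94 | 1.91 | 1.59 |
| Respiratory | 2.34 | 2.60 | 2.60 | 2.55 | 2.13 |
| Infectious | 23.76 | 26.40 | 26.40 | 25.92 | 21.60 |
| Hematologic | 2.55 | 2.83 | 2.83 | 2.78 | 2.32 |

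Only RR 0.80 matches all five printed values.

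**2. Does the crossing table belong to the same design?** I simulated the printed P boundaries as symmetric two-sided limits at information 0.25, 0.5, 0.75 and 1. The drift is the expected final Z.

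| Row | Drift | Simulated, interims 1 to 3 | Printed |
|---|---|---|---|
| Null | 0 | 0.075, 0.418, 0.838 | 0.08, 0.42, 0.84 |
| Alternative | 3.47 | 0.094, 0.402, 0.781 | 0.09, 0.40, 0.78 |
| Half-way | 1.735 | 0.062, 0.279, 0.631 | 0.06, 0.28, 0.63 |
| 1.5 times | 5.205 | 0.293, 0.813, 0.983 | 0.29, 0.81, 0.98 |

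Drift 3.47 gives 90.2% power, and drift −3.47 gives the same row. The table is that of the 90% design and does not depend on direction.

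**3. What would the other effects do to N?** For the average relative effect test, θ = |mean log odds ratio| / SE, with large-sample variances, equal arms (assumed from the alternating periods) and the printed saline incidences. At equal power, N scales as (θ at RR 0.80 / θ at the other RR)². At 4,274 per arm and correlation 0, θ is 3.006 (RR 0.80), 2.488 (RR 0.833) and 2.773 (RR 1.20).

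- RR 0.833: (3.006/2.488)² = 1.46; 8,548 × 1.46 ≈ 12,480.
- RR 1.20: (3.006/2.773)² = 1.175; 8,548 × 1.175 ≈ 10,040.

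At the protocol's correlation of 0.3 the ratios are 1.460 and 1.178, so N is about 12,480 and 10,070.

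A simpler check takes one component at a time, with n proportional to (p₁q₁ + p₂q₂)/(p₁ − p₂)². For infection at RR 0.80 this is (0.1943 + 0.1666)/0.0528² = 129.5; at RR 1.20, (0.1943 + 0.2164)/0.0528² = 147.3; at RR 0.833, (0.1943 + 0.1716)/0.0440² = 189.0. The ratios are 1.14 and 1.46. Across the five components they run from 1.14 to 1.22 and from 1.46 to 1.47.

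**4. What would a larger N do to power for the planned effect?** The drift grows with √N: 3.47 × √1.175 = 3.76 and 3.47 × √1.46 = 4.19. With the printed boundaries, power against RR 0.80 becomes about 94% and 97%.

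**5. Sensitivity.** Step 3 holds the saline incidences at their printed values. If they were instead re-derived from the same pooled rates under each increase reading (last two columns of the first table), the two arms would be the same pair of rates either way, 25.92% and 21.60% for infection. The ratio would then be about 1.49 for both: 8,548 × 1.49 ≈ 12,740.

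**Limit.** The stated 90% at 8,548 is not reproduced in closed form. A fixed-sample, two-sided, five-component calculation gives 59% at correlation 0.3 and 85% at correlation 0. The protocol used a simulation macro whose settings it does not give. I therefore rely on ratios and on the drift implied by the protocol's own crossing table, not on absolute closed-form power.

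**The case against.** The strongest reply is that this is loose wording with little numerical effect. Much of that stands.

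- The crossing probabilities are right. They reproduce from the 90% design and are the same in either direction, so only the label of the alternative is inconsistent.
- The back-up sentence names saline versus LR, so its direction agrees with the hypothesis; only the magnitude differs. The collapsed composite, with control rates from 26.4% to 34.3%, has at least 99.7% power at 4,274 per arm for RR 0.80, 0.833 or 1.20. The claim of more than 99% therefore holds on every reading for that analysis.
- The re-estimation is optional and conditional.
- The planned effect can be recovered from the printed incidences.

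A reader might also infer three stronger things that the protocol does not support.

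- That the pilot requires the data to be split by arm. The section does not say so. Its trigger names no arm, and the Sample size section already derives the saline rate from the overall rate. The method for the revised rate is simply left open.
- That the trial would lose power. No passage sizes 8,548 on RR 0.833 or 1.20, and following either reading would raise N.
- That a test would run in the wrong direction. The boundaries reproduce as symmetric two-sided limits, so the sign of the target affects the size of the trial and not the test.

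What the reply does not remove is the internal pilot sentence itself. It is a rule to be followed, and it names an effect that contradicts the design sentence, the hypothesis and the incidence table.

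**Conclusion.** The contradiction is real, and its consequence is confined to the internal pilot rule. If the re-estimation is used as written, the maximum would be about 17 to 18% too large (RR 1.20) or 46% too large (RR 0.833) for the design effect: about 10,050 or 12,480 against 8,548. The quarterly looks, and the boundaries attached to them, would move accordingly. The first look would fall at about 2,510 or 3,120 patients instead of 2,137. The result is a mis-sized trial, not an underpowered or reversed one.

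The sizes assume equal arms, the printed saline incidences, the average relative effect test and the same target power. They hardly depend on the correlation between components. The other two increase wordings are labels to tidy, with no number attached to them made wrong. The point should be corrected before the pilot look at about 1,000 patients, so that no choice of effect is made once data are in hand.

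**What to change.** In Internal pilot study, state the target of any second stage as a 20% relative decrease in complications for LR versus saline (RR 0.80). Add that the revised saline incidence is the pooled observed incidence divided by 0.9, the derivation behind the Sample size table. This settles the effect in advance and needs no data by arm.

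In Sample size, give the alternative of the crossing table and the effect in the back-up power sentence the same magnitude and reference arm. The printed probabilities, the power of more than 99% and the maximum of 8,548 are not changed by this correction.

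The cost is a few words in three places, with no new data and no new calculation.
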